9.2.4 Evaluation of non-target lesions

Complete Response (CR)	Requires all of the following: disappearance of all enhancing CNS non-target lesions, no new CNS lesions.
Non-CR/ Non-PD	Persistence of one or more non-target CNS lesion or lesions.
Progressive Disease (PD)	Any of the following: unequivocal progression of existing enhancing non-target CNS lesions, new lesion(s) (except while on immunotherapy-based treatment), or unequivocal progression of existing tumor-related non-enhancing (T2/FLAIR) CNS lesions. In the case of immunotherapy-based treatment, new lesions alone may not constitute progressive disease.

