2.2 Endpoints

2.2.1 Primary Endpoint

- Intracranial PFS is defined as the time from Day 1 of treatment until the criteria for intracranial disease progression is met as defined by RANO-BM or death as a result of any cause, whichever comes first.

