5. TREATMENT PLAN

This is a single arm, multicenter phase II trial for 60 patients with untreated extensive stage (ES) small cell lung cancer (SCLC) with asymptomatic brain metastases. Subjects will receive 4 cycles of induction treatment with Atezolizumab (1200 mg on Day 1) combined with carboplatin (5-6 AUC on Day 1) and etoposide (80-100 mg/m² on Days 1-3). Each cycle equals 21 days. After 4 cycles of induction treatment, subjects will receive atezolizumab maintenance 1200 mg on Day 1 of each 3-week cycle. Subjects will receive treatment until disease progression, unacceptable drug-related toxicity, or withdrawal from study for any reason.

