9.2.5 Evaluation of best overall CNS response

Target Lesions	Non-Target Lesions	New Lesions**	Corticosteroids	Clinical status	Overall Response
None	None	None	None	Stable or improved	CR
≥30% decrease in sum longest distance relative to baseline	Stable or improved	None	Stable or decreased	Stable or improved	PR
<30% decrease relative to baseline but <20% increase in sum longest distance relative to nadir	Stable or improved	None	Stable or decreased	Stable or improved	SD

$\geq 20\%$ increase in sum longest distance relative to nadir*	Uequivocal progressive disease*	Present*	N/A	Worse*	PD

*Progression occurs when any of these criteria are met. If ≤ 6 months from initiation of immunotherapy, radiographic progression (including new lesions) with no new or significantly worsened neurologic deficits not due to co-morbid event or concurrent medication should be confirmed on follow-up imaging 3 months after initial radiographic progression (if progression confirmed, the date of actual progression should be back-dated to the date of initial radiographic progression). **A new lesion is one that is not present on prior scans and is visible in minimum two projections. If a new lesion is equivocal, for example because of its small size, continued therapy can be considered, and follow-up assessment will clarify if the new lesion is new disease. If repeat scans confirm there is definitely a new lesion, progression should be declared using the date of the initial scan showing the new lesion.
					

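### While a patient is on atezolizumab, the same new brain lesion can be an iPFS event under section 9.2.5 and not under 9.2.4, and the protocol does not say which governs

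*Combined protocol and SAP*

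**What the plan says.** Section 2.2.1 starts the iPFS clock on the first treatment day and runs it "until the criteria for intracranial disease progression is met as defined by RANO-BM or death as a result of any cause"; section 12.2.1 repeats this. Section 9.2 is the protocol's only RANO-BM text, and it treats new lesions in two places.

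- **Section 9.2.4**, on non-target lesions, lists among the criteria for progression "new lesion(s) (except while on immunotherapy-based treatment" (the parenthesis closes there). It adds: "In the case of immunotherapy-based treatment, new lesions alone may not constitute progressive disease". It gives no time limit and no confirmation step.
- **Section 9.2.5**, on overall CNS response, has a separate New Lesions column. In the progression row the entry is Present, and the footnote says "Progression occurs when any of these criteria are met". At or before 6 months from the start of immunotherapy, "radiographic progression (including new lesions) with no new or significantly worsened neurologic deficits" is to be confirmed on imaging 3 months later and, if confirmed, back-dated to the first scan. For an equivocal lesion: "If repeat scans confirm there is definitely a new lesion, progression should be declared", again with the date of the first scan.

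Section 5 puts every patient on immunotherapy: "Subjects will receive 4 cycles of induction treatment with Atezolizumab (1200 mg on Day 1"), and then "After 4 cycles of induction treatment, subjects will receive atezolizumab maintenance 1200 mg on Day 1 of each 3-week cycle". No section says whether 9.2.4 or 9.2.5 prevails.

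**The concern.** The exemption in 9.2.4 is worded as an exception, but in this single-arm trial it covers every patient for as long as atezolizumab continues. Two readers following the protocol could code the same scan differently, one recording an iPFS event and the other none.

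The disagreement runs in one direction. A reader who follows 9.2.4 drops or postpones events that 9.2.5 would count, and never adds one. The sample size section (12.3) compares iPFS with a fixed 4.0-month historical median, so there is no concurrent control arm in which the same shift would occur. Section 9.2.4 is also unclear within itself: the parenthesis is categorical, while the following sentence is only permissive.

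**Working it through.** **1. The two rules side by side, for a patient on atezolizumab with stable or responding target lesions**

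| New brain lesion | 9.2.5 | 9.2.4 as written |
|---|---|---|
| At or before 6 months, no new or significantly worsened deficit, confirmed 3 months later | Progression, dated to the first scan | Exempt |
| After 6 months, unequivocal | Progression, no confirmation asked | Exempt |
| Equivocal, then confirmed on repeat scans | Progression, dated to the first scan | Exempt |

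Two records show the effect. (a) Targets are in partial response and unequivocal new metastases appear at month 8: 9.2.5 gives an event at month 8, and 9.2.4 gives none on that finding. (b) New metastases appear at week 15 without neurologic worsening and are confirmed 3 months later: 9.2.5 gives an event at week 15, and 9.2.4 gives none on that finding.

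No other row of 9.2.5 takes these patients. Complete response, partial response and stable disease all require no new lesions, so a patient with a confirmed new lesion fits only the progression row.

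**2. The plan's own design figures**

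Inputs from section 12.3: medians 4.0 and 5.2 months, 60 patients, 22 months' accrual, 12 months' further follow-up, exponential survival, one-sided 0.15. With λ = ln 2 / 4.0 = 0.1733 per month and uniform accrual:

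P(event) = 1 − (e^(−12λ) − e^(−34λ)) / (22λ) = 1 − (0.1250 − 0.0028) / 3.812 = 0.968.

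This gives 60 × 0.968 = 58.1 events, against the stated 0.9707 and 58. The power of a one-sample logrank test comes to 80-82% by normal approximation and simulation, against the stated 81% or so. The design figures are not in dispute.

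**3. What a switch from 9.2.5 to 9.2.4 could do**

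The test is Z = (O − E)/√E, with E = 0.1733 × total follow-up in months, rejecting when Z < −1.036. Event times are simulated under the null (median 4.0 months). A share q of events is assumed to be new-lesion-only. Under 9.2.4 each is replaced by a later event, with an exponential delay of mean d. Neither q nor d is in the documents.

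| Share q | Mean delay d (months) | Null rejection rate |
|---|---|---|
| 0 | none | 13-14% |
| 5-10% | 1-1.5 | 15-18% |
| 20% | 1-3 | 20-38% |
| 35% | 1.5-3 | 34% to about 60% |
| 50% | 1.5-3 | 45-80% |

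A harsher model never counts the new-lesion events, so the hazard is multiplied by 1 − q and the apparent median is 4.0/(1 − q). At q = 10% the median is 4.4 months and the rejection rate 39-40%; at q = 20% they are 5.0 months and 73-74%. At q = 1 − 4.0/5.2 = 23% the apparent median equals the 5.2-month target. For q = 20% the two models give 20-38% and 73-74%. That spread shows that the direction is fixed and the size is not.

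**The case against.** The best defence is structural. Section 9.2.4 rates one component, the non-target lesions, whereas 9.2.5 gives the overall response and has its own column for new lesions. Taking new lesions out of the component rating need not take them out of the overall rating. The 6-month footnote in 9.2.5 is written for patients on immunotherapy and names new lesions, so a blanket exemption would leave that clause without use in this trial. The permissive sentence in 9.2.4 can then be read as pointing to the confirmation step. This reading is plausible and is good reason to let 9.2.5 govern. It does not remove the unconditional parenthesis, and no sentence in the protocol adopts it.

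Three stronger readings are tempting, and the documents do not support them.

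- *New brain lesions never count in this trial.* The exemption holds only while the patient is on immunotherapy. Section 6.4 stops therapy at RECIST 1.1 progression, and section 9.1 counts a new lesion as progression. What follows is uncertain: after documented progression the study calendar moves to survival follow-up, and section 12 gives no censoring rule for iPFS.
- *Section 9.2.5 counts every new lesion at once.* It does not. Early lesions without neurologic worsening need confirmation, and equivocal lesions need repeat scans.
- *The 0.15 error rate is lost.* This would need the share of new-lesion-only events, a null known to be calibrated with new lesions counted, and readers who all apply 9.2.4. The documents give none of these. The null is attributed to IMpower133, where, according to section 1.4, patients with brain metastases had to have had cranial radiation.

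**Conclusion.** Wrong as written. Sections 9.2.4 and 9.2.5 give opposite answers for a confirmed new brain lesion, or an unequivocal one after 6 months, in a patient on atezolizumab, and this decides whether and when a primary-endpoint event occurs. This conclusion rests on the text alone.

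The direction is also firm: relative to 9.2.5, using 9.2.4 can only lengthen iPFS. The size is open. The rejection rates are illustrations that assume exponential times, a given share and delay, and 9.2.4 applied to every such lesion. They range from near the baseline rate for small shares and short delays to several times that rate for large ones. If sites already code by 9.2.5, the effect is small, but nothing in the protocol ensures that they do.

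**What to change.** State in section 9.2 that 9.2.5 with its footnotes (the 6-month confirmation and back-dating rule, and the equivocal-lesion rule) determines intracranial progression for iPFS. In 9.2.4, replace both the parenthesis and the permissive sentence with a cross-reference such as: *new lesions are assessed as in 9.2.5*. Add no further qualifier. A word such as *asymptomatic*, or a flat statement that new lesions are progression, would create a new mismatch with the 9.2.5 footnotes on neurologic deficits and equivocal lesions. Apply this single rule to all patients, including those already assessed, before the interim futility look and the final analysis.

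The cost is one wording change and a check of new-lesion assessments on existing scans. The downside is that an occasional inflammatory lesion appearing after 6 months will count as an event; before 6 months the confirmation step in 9.2.5 gives protection in patients without neurologic worsening.

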9.2.3 Evaluation of target lesions

Complete Response (CR)	Disappearance of all CNS target lesions sustained for at least 4 weeks; with no new lesions, no use of corticosteroids, and patient is stable or improved clinically.
Partial Response (PR)	At least a 30% decrease in the sum longest diameter of CNS target lesions, taking as reference the baseline sum longest diameter sustained for at least 4 weeks; no new lesions; stable to decreased corticosteroid dose; stable or improved clinically.

Progressive Disease (PD)	At least a 20% increase in the sum longest diameter of CNS target lesions, taking as reference the smallest sum on study (this includes the baseline sum if that is the smallest on study). In addition to the relative increase of 20%, at least one lesion must increase by an absolute value of 5 mm or more to be considered progression.
Stable Disease (SD)	Neither sufficient shrinkage to qualify for partial response nor sufficient increase to qualify for progressive disease, taking as reference the smallest sum longest diameter while on study.

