12.3 Sample Size and Accrual

The study will enroll 63 eligible patients who receive at least one dose of the study agent.

The sample size of the study is determined by the analysis of iPFS. To detect an improvement of median iPFS = 5.2 months from 4.0 months in historical control (IMpower 133) (HR = 0.77) using a logrank test, 60 treated patients will be required to achieve approximately 81% power at a one-sided significance level of 0.15. Patients are accrued for a period of 22 months. Follow-up continues for 12 months after the last patient is enrolled. The probability that a patient experiences an event during the study is 0.9707. The expected number of events during the study is 58. It is assumed that the survival time is exponentially distributed. The sample size calculation above is conducted in PASS v16.0.2. Assuming a 5% rate of dropout prior to protocol treatment, a total of 63 eligible patients will be treated by at least one doses of the study agent.

The sample size calculation is determined to have adequate power to reject the null hypothesis when the alternative hypothesis is true for the primary endpoint iPFS. Whether it has sufficient power for addressing secondary endpoints or exploratory analysis is not of concern.

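### Sections 9.2.4 and 9.2.5 conflict on whether a new brain lesion on atezolizumab is intracranial progression, so the primary endpoint can be scored two ways

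*Combined protocol and SAP*

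**What the plan says.** Sections 2.2.1 and 12.2.1 define iPFS as time from Day 1 to intracranial progression by RANO-BM or death from any cause. Neither says which part of section 9.2 decides whether a new lesion is an event.

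Section 9.2.4 lists among the non-target criteria for progression "new lesion(s) (except while on immunotherapy-based treatment" and then adds "In the case of immunotherapy-based treatment, new lesions alone may not constitute progressive disease". Under section 5, every patient receives atezolizumab until progression, unacceptable toxicity or withdrawal, so the exception covers all on-treatment time.

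In the overall CNS response table of 9.2.5, the presence of a new lesion is one of several starred entries in the progression row, and any one of them is enough. The footnote deals with the first 6 months of immunotherapy: radiographic progression, new lesions included, without new or clearly worse neurologic deficit is to be confirmed 3 months later and back-dated if confirmed. For an equivocal new lesion it says: "If repeat scans confirm there is definitely a new lesion, progression should be declared using the date of the initial scan showing the new lesion".

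For target lesions, 9.2.3 asks for a 20% increase and also that "at least one lesion must increase by an absolute value of 5 mm or more". The progression row of 9.2.5 gives only the 20%.

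The design in section 12.3 rests on iPFS: "To detect an improvement of median iPFS = 5.2 months from 4.0 months in historical control", for which "60 treated patients will be required to achieve approximately 81% power at a one-sided significance level of 0.15".

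**The concern.** The same patient can be an event under one section and event-free under the other, on the primary endpoint of an open-label, multicenter, single-arm trial. Sites may choose differently, and no control arm would carry the same scoring. Not counting new lesions can only lengthen iPFS, which is the direction of success against a fixed 4.0-month median.

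A lesion left uncounted may not be picked up later. Treatment stops on RECIST 1.1 progression (6.4), where a new lesion is progression (9.1.5 to 9.1.7). After documented progression the study calendar requires only survival follow-up, and section 1.4 allows standard treatment and radiation off study. Such a patient may have no further required brain MRI, which leaves death as the main remaining iPFS event. Section 12.2.1 gives no censoring rule for iPFS; 12.2.2 gives one for PFS only.

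**Working it through.** **1. The two rules side by side, for a patient on atezolizumab with an isolated new brain lesion**

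| Case | 9.2.4 | 9.2.5 |
|---|---|---|
| First 6 months, no new deficit, not yet confirmed | Not progression | Confirmation awaited |
| First 6 months, confirmed at 3 months | Not progression (exception) | Progression, back-dated |
| After 6 months, unequivocal | Not progression (exception) | Progression |

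Only the first row can be reconciled.

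**2. The plan's own power.** Inputs from 12.3: medians 4.0 and 5.2 months, 60 patients, one-sided 0.15, exponential times, 22 months' accrual, 12 months' follow-up. A one-sample log-rank test against the fixed exponential null gives 80.3% (81.3% simulated). The simple formula with 58 events is √58 × ln(5.2/4.0) − 1.036 = 7.616 × 0.2624 − 1.036 = 0.962, or 83.2%. The stated 81% therefore reproduces. (The stated event probability of 0.9707 fits 18 months' follow-up; 12 months gives 0.9348. With 18 months the power is 80.8%, so this does not affect the present point.)

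**3. Why a small shift matters.** With 58 events the test is positive at a hazard ratio below about exp(−1.036/√58) = 0.873, which is a median above about 4.0/0.873 = 4.58 months.

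**4. Effect of not counting isolated new lesions when the drug adds nothing.** Let s be their share of all first iPFS events, deaths included. The documents give no s, so it is an assumption. The null hazard is λ = ln 2/4.0 = 0.1733 per month.

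*(a) Never counted, other hazards unchanged.* The median is 4.0/(1 − s). It equals 5.2 at s = 1 − 4.0/5.2 = 23.1%.

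| s | Median (months) | Chance of a positive test |
|---|---|---|
| 0 | 4.00 | about 14% (nominal 15%) |
| 5% | 4.21 | 24-25% |
| 10% | 4.44 | 38-39% |
| 20% | 5.00 | 68-73% |
| 23.1% | 5.20 | 76-81% |

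The chances are simulated with 60 patients and 12 months' follow-up. The lower figure censors the patient at the new lesion; the higher keeps the patient at risk.

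*(b) A later countable event follows at k times the null hazard.* S(t) = e^(−λt) + s[e^(−λt) − e^(−kλt)]/(k − 1). At t = 5.2, e^(−λt) = 0.4061. For k = 2, 0.4061 + s(0.4061 − 0.1649) = 0.5 gives s = 39%. For k = 1 (where S = e^(−λt)(1 + sλt)), 1.5 and 3, the share needed is 26%, 32% and 55%. At k = 2, a 10% share gives a positive test in about 24% of trials.

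*(c) The event is only delayed by one scan.* S(5.2) = (1 − s) × 0.4061 + s × e^(−λ(5.2 − d)). For 6 weeks (d = 1.38 months), s = 0.0939/(0.5158 − 0.4061) = 86%. For 9 weeks (d = 2.07), s = 0.0939/(0.5814 − 0.4061) = 54%. At a 10% share the chance of a positive test is about 18% (6 weeks) or 20-22% (9 weeks).

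**5. The 5 mm condition.** A single target lesion growing from 10 to 12 mm has increased by 20% but by only 2 mm. It is progression by the 9.2.5 row and not by 9.2.3. Omitting the condition shortens iPFS, the opposite direction from the new-lesion exemption.

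**The case against.** The best defence is that the two sections can be read together. Section 9.2.4 assesses one component and also uses a permissive phrase; 9.2.5 is the overall table, and its footnote names new lesions on immunotherapy. On that reading a new lesion is not immediate progression, and confirmation decides. Under the exponential null, 1 − 0.5^(6/4) = 65% of events fall in the 6-month window. This stands in part: for unconfirmed early lesions the sections overlap, and a reader who infers flatly opposite rules goes too far. But the exception itself is flat. It still excludes a lesion that has been confirmed and any lesion after 6 months, and the permissive phrase leaves the choice to the site.

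A reader might also infer that the laxer rule would produce the whole target effect. The documents do not support that. The 23% figure needs the events never to be counted and other hazards to stay unchanged. Non-target growth, T2/FLAIR progression, clinical worsening and death still count. The denominator is all first events: if deaths were 20% or 40% of them (an assumption), the share needed among intracranial events would be 23.1/0.8 = 29% or 23.1/0.6 = 38%. The documents do not say how the historical control scored new lesions, so the net bias against it cannot be fixed.

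It is fair, too, that the RECIST stopping rule would ordinarily take such a patient off atezolizumab and so end the exception. The plan does not say how iPFS is scored afterwards, which adds to the ambiguity. Finally, 12.6.1 plans Kaplan-Meier estimates and confidence intervals, and the log-rank test appears only in 12.3 and 12.7. The error rates above refer to that test, but the median in 12.6.1 shifts in the same way.

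**Conclusion.** The point holds as a conflict in the definition of the primary endpoint and must be fixed. It rests on the wording alone: confirmed new lesions, and unequivocal ones after 6 months, are progression in 9.2.5 and excepted in 9.2.4, and nothing says which governs.

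The direction is certain: the laxer reading lengthens iPFS. The size is conditional on an undocumented share. A share of 10% of all first events would take the false-positive rate from about 14% to somewhere between about 18% (delay of one scan) and 39% (never counted). Moving the median all the way to 5.2 months needs 23% if never counted, 39% if a later event follows at twice the null hazard, and 54-86% if the event is only one scan late. All of this assumes exponential times and no drug benefit. The 5 mm mismatch is real but minor and runs the other way.

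**What to change.** State one new-lesion rule for iPFS and use it in 9.2.4, 9.2.5 and 12.2.1. One possible wording: an unequivocal new CNS lesion is progressive disease for iPFS, subject to the confirmation and back-dating rule in 9.2.5. The documents do not show which rule was intended, so the sponsor must choose; what matters is that the choice is single and made before the data are analysed.

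In the same place, state how a new lesion is scored for iPFS when confirmation is not obtained, when other therapy starts first, and when treatment has stopped on RECIST 1.1 progression, and give a censoring rule for iPFS. Report a sensitivity analysis under the other rule. Add the 5 mm condition to the target-lesion entry of the progression row in 9.2.5.

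The cost is protocol wording, a memo to sites and one extra analysis. Reported iPFS may be less favourable than under the exemption.

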9.2.5 Evaluation of best overall CNS response

Target Lesions	Non-Target Lesions	New Lesions**	Corticosteroids	Clinical status	Overall Response
None	None	None	None	Stable or improved	CR
≥30% decrease in sum longest distance relative to baseline	Stable or improved	None	Stable or decreased	Stable or improved	PR
<30% decrease relative to baseline but <20% increase in sum longest distance relative to nadir	Stable or improved	None	Stable or decreased	Stable or improved	SD

$\geq 20\%$ increase in sum longest distance relative to nadir*	Uequivocal progressive disease*	Present*	N/A	Worse*	PD

*Progression occurs when any of these criteria are met. If ≤ 6 months from initiation of immunotherapy, radiographic progression (including new lesions) with no new or significantly worsened neurologic deficits not due to co-morbid event or concurrent medication should be confirmed on follow-up imaging 3 months after initial radiographic progression (if progression confirmed, the date of actual progression should be back-dated to the date of initial radiographic progression). **A new lesion is one that is not present on prior scans and is visible in minimum two projections. If a new lesion is equivocal, for example because of its small size, continued therapy can be considered, and follow-up assessment will clarify if the new lesion is new disease. If repeat scans confirm there is definitely a new lesion, progression should be declared using the date of the initial scan showing the new lesion.
					

